Efficacy assessment(s)	
Response to treatment and disease progression will be assessed by PE, specifically assessing changes in spleen length by palpation. Disease assessment will be performed at screening/baseline, month 1, 2 month 3, and every 3 months thereafter; and at discontinuation of study drug.
 
In patients without splenomegaly, efficacy assessments will only be provided by the patient reported outcomes that measures symptoms of the disease.

Special safety assessment(s)	AEs of all grades, Grade 3/4 AEs, SAEs; laboratory assessments (hematology, serum chemistry, coagulation), vital signs (blood pressure, heart rate, respiratory rate, temperature); cardiac assessments.
Patient reported outcomes	The FACT-Lym (version 4) and the FACIT-Fatigue Scale will be used to document patient reported symptoms including physical well-being, social/family well-being, emotional well-being, functional well-being, constitutional symptoms and fatigue.
Medical Resource Utilization	MRU will be collected up to week 48 to document number of hospitalizations, emergency room visits, outpatient office visits general practitioner, specialist, urgent care visits; transfusions; concomitant medications; and splenectomy/splenic irradiation.
Pharmacokinetics	N/A
Biomarker assessments	N/A

Exploratory Biomarker pharmacodynamic studies involving tumor samples	N/A
Optional Biomarker studies on additional or remaining samples	N/A
DMC	Not applicable
Statistical methods and data analysis	
The primary study objective (to collect safety data) and secondary objective being descriptive; only descriptive statistics will be provided.
 
Data from all centers will be combined and analyzed together.
 
The primary analysis will be performed after all patients have either completed 24 months of treatment or have been prematurely discontinued from the study.
 
Analysis sets: Full Analysis Set (FAS) consists of all patients who received at least one administration of study drug.
 
Safety set consists of all patients who received at least one dose of study drug and had at least one post-baseline safety assessment.
 
Per protocol set: consists of all FAS patients without any major protocol deviation. Rules for identifying major protocol deviations would be detailed in Report Analysis Plan.
 
Analysis methods Primary objective The analysis will provide the incidence of treatment-emergent AEs (occur during treatment, including the 28 safety follow-up days) or AEs that worsen on treatment. Death rate (any death) at end of study will be summarized.
 
Secondary objectives: Efficacy The proportion of patients by best overall response category will be summarized. Proportion of responders will be estimated and its 95% confidence intervals provided.
 
 - Change in spleen length from Baseline to end of each visit/month of therapy and at end of treatment will be described using descriptive statistics and by relevant change categories. - Change in WBC and platelet count changes from Baseline to end of each visit and at end of treatment. - Shift in fibrosis in the bone marrow from Baseline to worst/best value on study will be described. - PFS, LFS, and OS will be estimated with the Kaplan Meier method and 95% confidence intervals will be provided for the estimated median. 
Secondary objectives: MRU Frequency of hospitalization, of emergency room visits, general practitioner, specialist, or urgent care visits,, and of splenectomy and splenic irradiation will be summarized at end of each treatment quarter.
 
Overall duration of hospitalization at end of study will be summarized
 
The proportion of patients who are transfusion dependent as well as the proportion of patients whose transfusion status (dependent or independent) changed (from dependent

	
to independent or vice versa) will be tabulated with summary statistics.
 
Quality of Life Assessments
 
ECOG score will be summarized descriptively by visit. A shift summary including number and % of patients will be produced by visit for baseline vs. post-baseline scores.
 
Data from FACT-Lymphoma (version 4) Scores will be analyzed in the sum scores. Change and % change from baseline to each scheduled visit will be calculated. The treatment effect on FACT-Lymphoma Scores over time will be estimated using repeated measurements analysis.
 
Data from FACIT Scores will be analyzed in the sum scores. Change and % of change from baseline to each scheduled visit.
 
Time to first improvement will be estimated for ECOG performance score and for selected scales for FACT-Lymphoma (version 4) and FACIT scale according to minimally important difference (MID).
 
[REDACTED]
 
[REDACTED]

Interim analysis (IA)	
An interim analysis will be performed to closely monitor safety, and ensure an appropriate risk/benefit ratio in the patient population with low platelet counts, between 50,000 and <100,000/μL /μL. In order to adequately assess the risk/benefit ratio, this analysis will also be performed on a non-low platelet population (patients with baseline platelet count \geq100,000/μL), which will be further detailed in analysis plan, who will serve as an internal reference population. This interim analysis will take place when 50 patients with low platelets have completed 6 months of treatment
 
Analyses will also be performed if needed to fulfill regulatory obligation, to comply with post-approval commitments or for publication purpose.

1 Background

[figure not shown]
INC424 phosphate is an inhibitor of the Janus kinase family of protein tyrosine kinases (JAKs) that is currently under development for treatment of primary myelofibrosis (PMF), post polycythemia vera myelofibrosis (PPV MF) and post essential thrombocythemia myelofibrosis (PET-MF). INC424 (ruxolitinib, Jakafi®) was approved by the FDA on 16 November 2011, and approved by the EMA on 31 August 2012, for the treatment of intermediate or high-risk myelofibrosis, including primary myelofibrosis, post-polycythemia vera myelofibrosis and post-essential thrombocythemia myelofibrosis.

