	
 - Changes in vital signs. 
Quality of Life (See Table 7-1 for assessments).
 
 - Change in ECOG PS from Baseline to each visit where measured. 
Change in Functional Assessment of Cancer Therapy for patients with Lymphoma (FACT-Lym) version 4 from Baseline to each visit where measured (See Appendix VII).
 
 - Change in Functional Assessment of Chronic Illness Therapy (FACIT) Fatigue from baseline to each visit where measured (See Appendix VIII). 
Medical resource utilization (MRU) Medical resource utilization (MRU) will be assessed as follows:
 
 - Frequency and duration of hospitalization from Baseline up to week 48 of therapy - Frequency of emergency room visits from Baseline up to week 48 of therapy. - Frequency of general practitioner, specialist, and urgent care visits from Baseline up to week 48 of therapy. - Number of transfusions and transfusion dependency status end of study. - Splenectomy and use of splenic irradiation. - Changes in use of concomitant medications for MPN symptom management (Appendix IX).
Endpoints (efficacy)	
Efficacy data will be collected.
 
 - Best overall response to treatment as assessed by spleen palpation (calculated as the percentage change in spleen length compared with Baseline). - Change in spleen length from Baseline to end of each visit. - Change in WBC and platelet count changes from Baseline to end of each visit/month of therapy and at end of treatment. - Shift in fibrosis in the bone marrow from Baseline to worst/best value on study (where bone marrow biopsies are performed – not mandatory). - Progression free survival, acute myeloid leukemia free survival and overall survival. - In patients without splenomegaly, patient reported outcomes measure symptoms of the disease.

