6.3 Concomitant medications

All concomitant medications and treatments must be recorded on the appropriate eCRF. Any prior medication received up to 30 days prior to the first dose of study drug will be recorded in the CRF. All prior medications used to treat (record applicable indication) disease will be recorded. Patients will be instructed not to take any additional medications (including over-the-counter products) during the course of the study without consultation with the investigator.

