Prior medications are defined as drugs taken and stopped prior to first dose of study medication. Any medication given at least once between the day of first dose of study medication and the last day of study visit will be a **concomitant** medication, including those which were started pre-baseline and continued into the treatment period.

Prior and concomitant medications will be summarized in two separate tables.

Missing and incomplete start date for concomitant medications will be imputed according to Novartis conventions described in [\[RAP Module 8\]](#).

No imputation algorithm will be applied to any missing stop date.

Table 1-1 Allocation of concomitant medications

If	Concomitant medication
Start date ≤ study drug start date AND Stop > study drug start date OR Stop=missing OR ongoing	X
Start > study drug start date	X

Prior medications to treat MF

Prior medications to treat PMF, PPV MF, or PET-MF will be recorded including regimens discontinued up to 30 days prior to the study entry. This information will be summarized by ATC class and preferred term, and best response on last therapy will be summarized separately.

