3.6 Resource Utilization

Frequency of hospitalization, of emergency room visits, general practitioner, Specialist, urgent care, splenectomy and splenic irradiation will be summarized at end of each quarter (i.e. every three months after start of study medications).

Overall duration and number of hospitalization at the end-of-study will be summarized.

Change in blood transfusion dependency

The proportion of patients who are transfusion dependent as well as the proportion of patients, whose transfusion status (dependent or independent) changed (from dependent to independent or vice versa) , will be tabulated with summary statistics. For the purposes of this assessment

- **Transfusion dependence at baseline** will be defined as patient who received 6 or more units of red blood cell product(s) during the 12 weeks prior to first study drug administration.
- **New onset of transfusion dependence** will be defined as the use of 6 or more units of red blood cell product(s) during any consecutive 12 weeks prior to end of study for patients who were not transfusion dependent at baseline.
- **New transfusion independency** will be defined as no (0) use of red blood cell product(s) during any consecutive 12 weeks prior to end of study for patients who met the definition of transfusion dependence at baseline.
- **Transfusion dependence response:** will be defined as the use of 5 or less units of red blood cell product(s) during any consecutive 12 weeks prior to end of study for patients who were transfusion dependent at baseline.

Patients who were not transfusion-dependent at baseline and who required transfusions during the study, but not during the last 12 weeks of observation, will be considered transfusion independent.

The number and percent of patients who received any blood component transfusions will be summarized by blood component (PRBC (Packed Red Blood Cells), platelets), and visit when the transfusion data were collected.

Prior and concomitant medications, as listed in protocol Appendix IX will be summarized.

Concomitant medication at week 24, as listed in protocol Appendix IX, will be summarized.

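### The endpoint is a change in use of Appendix IX symptom medications, but no planned table estimates a change

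*Protocol*

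**What the plan says.** The protocol synopsis and section 3.3.4 name the endpoint as "Changes in use of concomitant medications for MPN symptom management (Appendix IX"). It serves the secondary objective of documenting MRU.

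For its analysis, SAP 3.6 states: "Prior and concomitant medications, as listed in protocol Appendix IX will be summarized". SAP 3.6 and protocol 11.6.4.1 both add a summary of the Appendix IX drugs at Week 24.

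SAP 3.3 supplies the definitions:

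- *Prior*: "Prior medications are defined as drugs taken and stopped prior to first dose of study medication".
- *Concomitant*: "Any medication given at least once between the day of first dose of study medication and the last day of study visit", "including those which were started pre-baseline and continued into the treatment period".
- Layout: "Prior and concomitant medications will be summarized in two separate tables".
- Missing dates: "No imputation algorithm will be applied to any missing stop date". SAP Table 1-1 counts a drug with a missing stop date as concomitant.

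On collection, protocol 6.3 says: "Any prior medication received up to 30 days prior to the first dose of study drug will be recorded in the CRF". Drugs used to treat the disease itself are recorded without that limit. Protocol 8.3.3 ends MRU collection at 48 weeks. SAP section 4 lists only the transfusion definitions as changes to the protocol analyses.

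**The concern.** A change needs use before treatment and use on treatment, measured by one rule in the same patients. The patients who carry the information are those taking a symptom drug when INC424 starts, because they either stop it or continue. The SAP 3.3 definitions remove them from the prior table and hold them in the concomitant table either way. No table reports how many they were.

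The endpoint would therefore go unanswered although the data exist. A reader looking for a before-and-after picture would find only the prior and concomitant tables, and they cannot provide it.

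Other items in the same plan do have a change analysis. SAP 3.6 defines categories for change in transfusion status, and SAP 3.4.4 plans a baseline-by-visit shift table for ECOG score.

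**Working it through.** The documents give no rate of use for any Appendix IX drug, so there is no figure of the plan's own to reproduce. The check applies the SAP 3.3 definitions to assumed rates.

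**Notation (all rates are assumptions)**

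- b: share of patients using a drug at first dose and continuing past it
- s: share who took it in the look-back period and stopped before first dose
- f: share of the b group who stop on treatment before Week 24
- n: share of non-users at first dose who start on treatment; half of these are taken to be users at Week 24

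The Week 24 summary is read as drugs in use at Week 24. Drop-out is ignored.

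**What each table shows**

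- Prior = s
- Concomitant = b + (1 − b)n
- Week 24 = b(1 − f) + (1 − b)n/2
- Change the endpoint asks for = Week 24 − b

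The concomitant share has no f in it, so it cannot register stopping. The Week 24 share does contain f, but b appears in no table.

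**Effect of stopping, with b = 60%, s = 10%, n = 15%**

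Concomitant = 0.60 + 0.40 × 0.15 = 66% at every value of f. Week 24 use is:

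- f = 0: 0.60 + 0.03 = 63%
- f = 50%: 0.30 + 0.03 = 33%
- f = 100%: 0 + 0.03 = 3%

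For f = 50%, and taking all 2238 enrolled patients, the tables would show prior 10% (224), concomitant 66% (1477) and Week 24 33% (739). The starting value of 60% is missing. Prior to concomitant looks like a rise of 66 − 10 = 56 points. The actual change is 33 − 60 = −27 points.

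**Range of assumptions**

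| b | s | f | n | Actual use, first dose to Week 24 | Prior | Concomitant |
|---|---|---|---|---|---|---|
| 60% | 10% | 50% | 15% | 60% to 33% | 10% | 66% |
| 30% | 10% | 50% | 10% | 30% to 18.5% | 10% | 37% |
| 10% | 5% | 50% | 5% | 10% to 7.25% | 5% | 14.5% |
| 5% | 30% | 50% | 5% | 5% to 4.9% | 30% | 9.8% |

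Prior to concomitant rises only if s < b + (1 − b)n. The last row fails that condition and shows no rise.

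A grid of assumed rates (b 5–70%, s 2–30%, f 25–90%, n 0–30%) contains 670 combinations in which use truly falls. Prior to concomitant rises in 599 of them (89%), and by at least 20 points in 72%. The Week 24 share exceeds the prior share in 61%. These are shares of a chosen grid, not probabilities.

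**Unequal windows**

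For a short-course drug at a constant rate of one course a year, the share with any use in d days is 1 − exp(−d/365.25). That is 7.9% for the 30-day look-back and 60.1% for the 336 days to Week 48, with no change in the rate of use.

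**The case against.** The strongest reply is that the plan never sets prior against concomitant. SAP 3.3 puts them in two separate descriptive tables, and no difference is to be calculated. This stands. A reader might infer that the plan will display a real fall as a large rise. The documents do not support that: the rise appears only if someone compares the tables, and its sign and size depend on rates that are not given.

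Second, the Week 24 summary does react to stopping. This also stands. What it lacks is a baseline counterpart.

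Third, a reader might suppose that concomitant use accumulates over the whole study, from August 2011 to December 2016. MRU is collected only to Week 48 (protocol 8.3.3 and the synopsis), so that argument should not be pressed. SAP 3.6 does not repeat the limit and could usefully do so. Nor is the look-back 30 days for everything, since drugs for the disease are recorded without that limit.

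Fourth, the protocol uses *prior* more loosely. Section 11.4 speaks of medications before and after the start of study drug, and section 6.3.1 records everything taken in the 30 days before entry. On that usage, drugs ongoing at first dose would count as prior. SAP 3.3 is the operative definition, however, and even the looser one gives any use in a look-back period, not use at baseline.

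Fifth, blood products in Appendix IX are partly covered by the transfusion analyses in SAP 3.6. That leaves the drugs uncovered.

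**Conclusion.** The point holds as a gap between endpoint and analysis. Followed exactly, the plan produces no figure for use at baseline and no estimate of change. The concomitant table cannot register stopping under any rates, because this follows from the definitions alone. The Week 24 table can, but has nothing to be compared with. If prior and concomitant were compared, they would usually, though not always, suggest a rise even when use falls. That part rests on assumed rates and on reading the Week 24 summary as point use.

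The importance is minor. This is one descriptive item under a secondary objective to document resource use, and no primary or safety conclusion depends on it.

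**What to change.** In SAP 3.6:

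- Define baseline use as an Appendix IX drug in use on the day before first dose. Apply the same rule on the study day of Week 24 and of Week 48, where MRU collection ends.
- Present a paired shift table (used or not at baseline, by used or not at the visit) for each Appendix IX indication, among patients still on study at that visit. Give the numbers who stopped and who started.
- State how a drug with a missing stop date is classified at each time point.
- Report separately any Appendix IX drug whose stopping the protocol itself requires. Anagrelide is one: it is listed in Appendix IX and also in protocol 6.3.3. Its disappearance is not a treatment effect.
- State that the prior and concomitant tables do not measure change.

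SAP 3.3 also needs a small reconciliation. A drug stopped on Day 1 is concomitant by the text but not by Table 1-1, which requires a stop date after the start of study drug.

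The cost is one SAP paragraph and one table. Start and stop dates already drive Table 1-1, so no new data are needed. The drawback is that each shift table is conditional on patients still on study at that visit, so the number contributing should be shown.

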Study design	
This is a multicenter, single-arm, open-label expanded access study intended to provide additional data on the safety and efficacy of INC424 in patients with PMF, PPV MF, or PET-MF who have either previously received treatment or have not received treatment. All patients will be screened using inclusion and exclusion criteria (Section 5.2 and Section 5.3) within 28 days prior to the first dose of INC424. See Table 7-1 for a description of the screening evaluations required.
 
Baseline evaluations should be performed within 7 days of the first dose of INC424, however platelets should be performed within a maximum of 4 days of the first dose of INC424.
 
Subsequently, patients will be asked to visit the clinic monthly for the first 3 months, then every 3 months thereafter, and at study discontinuation.
 
All patients will be treated for PMF, PPV MF, or PET-MF in each participating country with

	
oral INC424 at a dose of 5 - 25 mg (dose based on Baseline platelet count) BID until either:
 
 - Disease progression; - Transplant; - Unacceptable toxicity; - Death; - Discontinuation from the study for any other reason; - Withdrawal of consent; - Physician decision; - Until 24-months after LPFV; or - Until the drug is commercially available, whichever occurs first. 
The FPFV occurred on 16 August 2011 and the recruitment period ended on 31 Dec 2014. The study enrolled a total of 2238 patients. The last patient last visit is expected in December 2016.

Population	
Male or female patient's \geq 18 years of age with a diagnosis of PMF, PPV MF, or PET-MF will be enrolled. Eligible patients who have either never received treatment, or who have received prior treatment with commercially available agents (e.g., busulfan, danocrine [danazol[®], hydroxyurea, anagrelide, lenalidomide] or have previously received investigational drug may be enrolled. Patients must meet all inclusion and none of the exclusion criteria within 4 weeks prior to the first dose of INC424.
 
All prior treatment for PMF, PPV MF, or PET-MF must be discontinued prior to Day 1 of INC424, and all AEs attributed to these treatments must be resolved prior to Day 1 of INC424 treatment.
 
This study will be conducted worldwide, excluding USA.

Sample Size	
The projected number of patients that will be treated in this study is a maximum of 2500 patients.

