	
14. Pregnant or nursing (lactating) women, where pregnancy is defined as the state of a female after conception and until termination of gestation, confirmed by a positive βHCG laboratory test (> 5 mIU/mL).
 
15. Women of child-bearing potential, defined as all women physiologically capable of becoming pregnant, unless they are using highly effective methods of contraception throughout the study duration inclusive of 28 day safety follow up. Highly effective contraception methods include:
 
Total abstinence (when this is in line with the preferred and usual lifestyle of the subject). Periodic abstinence (e.g., calendar, ovulation, symptothermal, post-ovulation methods) and withdrawal are not acceptable methods of contraception
 
Female sterilization (have had surgical bilateral oophorectomy with or without hysterectomy), total hysterectomy or tubal ligation at least six weeks before taking study treatment. In case of oophorectomy alone, only when the reproductive status of the woman has been confirmed by follow up hormone level assessment
 
Male sterilization (at least 6 months prior to screening). the vasectomized male partner should be the sole partner for that subject.
 
Use of oral, injected or implanted hormonal methods of contraception or placement of an intrauterine device (IUD) or intrauterine system (IUS) or other forms of hormonal contraception that have comparable efficacy (failure rate $<1\%$), for example hormone vaginal ring or transdermal hormone contraception
 
Women are considered post-menopausal and not of child bearing potential if they have had 12 months of natural (spontaneous) amenorrhea with an appropriate clinical profile (e.g. age appropriate, history of vasomotor symptoms) or have had surgical bilateral oophorectomy (with or without hysterectomy), total hysterectomy or tubal ligation at least six weeks ago. In the case of oophorectomy alone, only when the reproductive status of the woman has been confirmed by follow up hormone level assessment is she considered not of child bearing potential.
 
Women of child-bearing potential, defined as all women physiologically capable of becoming pregnant, including women whose career, lifestyle, or sexual orientation precludes intercourse with a male partner and women whose partners have been sterilized by vasectomy or other means, UNLESS they are using highly effective contraception methods (see) defined as:
 
- Total abstinence and- Female sterilization- Combination of any two of the following (a+b or a+c or b+c):
(a) Use of oral, injected or implanted hormonal methods of contraception(b) Placement of an intrauterine device (IUD) or intrauterine system (IUS)(c) Barrier methods of contraception: Condom or Occlusive cap (diaphragm or cervical/vault caps) with spermicidal foam/gel/film/cream/ vaginal suppository 
- The duration of required highly effective contraception is: during dosing and for 5 times the terminal half-life of INC424 (i.e. 29 hours). The mean elimination half-life of INC424 is approximately 3 hours and the mean half-life of INC424 and metabolites is approximately 5.8 hours.
 
16. Patients who are unable to comprehend or are unwilling to sign an ICF.
 
17. Patients with active alcohol or drug addiction that would interfere with their ability to comply with the study requirements.
 
18. Patients with any concurrent condition that, in the Investigator's opinion, would

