
Treatment period (open): All patients who consent to study participation will start treatment with INC424 upon meeting all study eligibility criteria. The study period commences on Day 1 (day of first dose of study drug) and continues until either:

- a. Disease progression;
- b. Transplant;
- c. Unacceptable toxicity;
- d. Death;
- e. Discontinuation from the study for any other reason;
- f. Physician decision
- g. Withdrawal of consent;
- h. Until 24-months after LPFV; or
- i. Until the drug becomes commercially available, whichever occurs first

[figure not shown]
Should INC424 not be available to patients after the drug is commercialized or 24-months after LPFV, Novartis will have a local transition plan in place to ensure that patients have access to INC424 without delays to treatment. Once the last dose of INC424 open label study drug is taken, or it becomes commercially available in each participating country or 24-months after LPFV, no further AEs/SAEs will be collected after the required Study Completion (see [Section 7.6.3](#)).

End of study / treatment: Day of last dose of open-label INC424.

Follow-up period: 28 days following the last dose of open-label INC424.

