15. Women of child-bearing potential, defined as all women physiologically capable of becoming pregnant, unless they are using highly effective methods of contraception throughout the study duration inclusive of 28 day safety follow up. Highly effective contraception methods include:

[figure not shown]
- Total abstinence (when this is in line with the preferred and usual lifestyle of the subject). Periodic abstinence (e.g., calendar, ovulation, symptothermal, post-ovulation methods) and withdrawal are not acceptable methods of contraception
- Female sterilization (have had surgical bilateral oophorectomy with or without hysterectomy), total hysterectomy or tubal ligation at least six weeks before taking study treatment. In case of oophorectomy alone, only when the reproductive status of the woman has been confirmed by follow up hormone level assessment
- Male sterilization (at least 6 months prior to screening). The vasectomized male partner should be the sole partner for that subject.
- Use of oral, injected or implanted hormonal methods of contraception or placement of an intrauterine device (IUD) or intrauterine system (IUS) or other forms of hormonal contraception that have comparable efficacy (failure rate <1%), for example hormone vaginal ring or transdermal hormone contraception

Women are considered post-menopausal and not of child bearing potential if they have had 12 months of natural (spontaneous) amenorrhea with an appropriate clinical profile (e.g. age appropriate, history of vasomotor symptoms) or have had surgical bilateral oophorectomy (with or without hysterectomy), total hysterectomy or tubal ligation at least six weeks ago. In the case of oophorectomy alone, only when the reproductive status of the woman has been confirmed by follow up hormone level assessment is she considered not of child bearing potential.

16. Patients who are unable to comprehend or are unwilling to sign an ICF

17. Patients with active alcohol or drug addiction that would interfere with their ability to comply with the study requirements

18. Patients with any concurrent condition that, in the Investigator's opinion would jeopardize the safety of the patient or compliance with the protocol.

19. In the case of ruxolitinib pretreated patients, ruxolitinib primary resistant patients defined as:

- No spleen reduction within the first 12 weeks after front line therapy with ruxolitinib. AND

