14.2 Appendix II - Information regarding highly effective contraception methods

Highly effective contraception methods include:

- Total abstinence (when this is in line with the preferred and usual lifestyle of the subject). Periodic abstinence (e.g., calendar, ovulation, symptothermal, post-ovulation methods) and withdrawal are not acceptable methods of contraception
- Female sterilization (have had surgical bilateral oophorectomy with or without hysterectomy), total hysterectomy or tubal ligation at least six weeks before taking study treatment. In case of oophorectomy alone, only when the reproductive status of the woman has been confirmed by follow up hormone level assessment
- Male sterilization (at least 6 months prior to screening). The vasectomized male partner should be the sole partner for that subject.
- Use of oral, injected or implanted hormonal methods of contraception or placement of an intrauterine device (IUD) or intrauterine system (IUS) or other forms of hormonal contraception that have comparable efficacy (failure rate <1%), for example hormone vaginal ring or transdermal hormone contraception (in case of oral contraception you should have been using the same pill on a stable dose for a minimum of 3 months before screening)

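### Synopsis exclusion criterion 15 states two conflicting contraception rules: the Amendment 5 text, which section 5.3 repeats, and a leftover block that ends the duty 29 hours after dosing

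*Protocol*

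**What the plan says.** In the synopsis, criterion 15 opens with the Amendment 5 text. Women of childbearing potential are excluded "unless they are using highly effective methods of contraception throughout the study duration inclusive of 28 day safety follow up". The list that follows joins hormonal methods, IUD and IUS by 'or', so one is enough, and it accepts a partner vasectomized at least six months before screening if he is the sole partner.

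After a paragraph on post-menopausal status, the same criterion starts again. The restarted definition also covers "women whose partners have been sterilized by vasectomy or other means, UNLESS they are using highly effective contraception methods (see) defined as", and the cross-reference in it is empty. Apart from abstinence and female sterilization, it requires this: "Combination of any two of the following (a+b or a+c or b+c". The three classes are hormonal methods, IUD/IUS and barrier methods. It then fixes the duration: "The duration of required highly effective contraception is: during dosing and for 5 times the terminal half-life of INC424 (i.e. 29 hours".

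The body of the protocol carries one rule:

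- Section 5.3, criterion 15, requires contraception "throughout the study duration inclusive of 28 day safety follow up" and has neither the two-method nor the 29-hour text.
- Appendix II gives the same method list, including "Male sterilization (at least 6 months prior to screening). The vasectomized male partner should be the sole partner for that subject". It adds one condition that section 5.3 lacks: an oral contraceptive should have been the same pill at a stable dose for at least three months before screening.
- Section 4.1 sets the follow-up period at "28 days following the last dose of open-label INC424".
- Section 9.3 requires reporting of pregnancies up to 28 days after the drug is stopped.

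**The concern.** A site that reads the synopsis gets two answers to two practical questions: when an enrolled woman may stop contraception after her last dose, and whether one method or a vasectomized sole partner is enough while she is on treatment.

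The rule still matters although recruitment has ended. The Amendment 5 rationale says that the updated wording may be used for women already enrolled, and last patient last visit is expected in December 2016. Section 1.3.5 describes the drug as embryotoxic and foetotoxic in animals, says that the human risk is unknown, and contraindicates use in pregnancy. A pregnancy precaution should be readable in one way only.

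The synopsis also lists failure to use adequate birth control among the reasons for which a patient may be removed. That bears on the choice of method during treatment. It does not bear on the conflict over duration, because both blocks require contraception while the drug is being taken.

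**Working it through.** **The plan's own figure.** The second block gives a mean half-life of about 3 hours for the parent drug and about 5.8 hours for drug and metabolites.

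- 5 × 5.8 h = 29 h, which reproduces the stated figure; 29 / 24 = 1.2 days.
- With the parent half-life the result would be 5 × 3 h = 15 h, so the 29 hours rests on drug plus metabolites.

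**Size of the conflict over duration.** The other end point is the 28 days in the first text of criterion 15, in section 5.3 and in section 4.1.

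- 28 × 24 = 672 h.
- 672 − 29 = 643 h; 643 / 24 = 26.8 days.
- 672 / 29 = 23.2, so one stated duration is about 23 times the other.

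**Side by side.**

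| Item | First text (also section 5.3) | Second block (synopsis only) |
|---|---|---|
| End of duty | 28 days after last dose | 29 hours after dosing |
| Hormonal method alone, or IUD/IUS alone | Enough | Not enough; two classes needed |
| Vasectomized sole partner | Accepted method | Woman still needs a listed method |
| Abstinence or female sterilization | Accepted | Accepted |

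**Test cases.**

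1. IUD alone through day 28: meets the first text, fails the second block.
2. Vasectomized sole partner and nothing else: meets the first text, fails the second block.
3. Hormonal method plus condom, stopped two days after the last dose: meets the second block, fails the first text.
4. Hormonal method plus condom through day 28: meets both.

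Neither rule contains the other. The second block is tighter on method, since each permitted pair includes a hormonal method or an IUD/IUS and so also satisfies the first list. It is looser on duration.

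**Which rule was intended.** Section 5.3 carries only the first rule. Appendix II carries its method list and no trace of the two-method rule. Sections 4.1 and 9.3 both use 28 days. The Amendment 5 log, read here for intent only, says that synopsis criterion 15 was brought up to current guidance and that the eligibility checklist was dropped to avoid confusion over contraception. The restarted definition and the empty cross-reference look like text that should have been removed.

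**The case against.** The strongest reply is that the working text is already right. The synopsis itself sends sites elsewhere for the criteria: "All patients will be screened using inclusion and exclusion criteria (Section 5.2 and Section 5.3". The counselling step in section 7.3 refers to Appendix II. Neither section 5.3 nor Appendix II contains the second block. This stands and is the main reason why the impact is small. It does not remove the conflict: the synopsis is part of the protocol, and I find no statement that the body takes precedence over it.

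The second block may also be struck-through text that was read as plain text. That cannot be fully excluded from the extracted copy. It is unlikely, because Amendment 5 places strike-through in a separate track-changes version and section 5.3, edited in the same amendment, shows no such residue. That the block is older is likewise an inference.

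The 643 hours has little clinical weight. It starts after five of the half-lives stated in the block, when (1/2)^5 = 1/32, about 3%, of drug and metabolites would remain under simple exponential elimination. That is fair; the figure measures how far the texts disagree and nothing more.

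Finally, a change of text is not free. Section 12.11 requires a written amendment approved by the sponsor, the ethics bodies and, where required, health authorities. That stands, and it shapes the fix.

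**Conclusion.** The inconsistency is real and lies wholly within current text. Synopsis criterion 15 holds two rules that differ on duration (29 hours against 28 days, a gap of 643 hours), on the number of methods, and on the vasectomized partner. Section 5.3 holds only the first.

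The impact is minor. Enrollment closed on 31 December 2014. Few women are likely to be affected: section 1.1 puts the median age at diagnosis at about 65 years, though the documents give no count of enrolled women of childbearing potential. No endpoint, analysis set or sample size is involved.

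A reader might go further and infer that the protocol leaves women without a contraception requirement for almost 27 days, or that patients were put at risk. The documents do not support either. The 28-day sentence opens the same criterion, so the requirement is contradicted and not absent. Two methods used through day 28 satisfy both blocks. No pregnancy or instruction error is shown, and the consent form, which carries what patients are told, is not in the copy reviewed.

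The conclusion assumes that both blocks are live text in the issued synopsis and that the second is a leftover.

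**What to change.** Delete the second block from synopsis criterion 15, from the point where the definition of childbearing potential restarts through the sentence that gives the 5.8-hour half-life, so that the synopsis matches section 5.3. Under section 12.11 this needs a written amendment; fold it into the next one, since the edit alone does not justify an amendment cycle.

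Meanwhile, send sites with women of childbearing potential on treatment a short clarification that section 5.3 criterion 15 governs, both for the method list and for the 28-day duration. Name section 5.3 alone as the reference, because Appendix II adds the three-month stable-pill condition and the two lists are therefore not identical. The clarification restates a rule that is already in the approved protocol.

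The cost is one deletion within an amendment and one site notice, with no effect on data collection or analysis.
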